1 INTRODUCTION

This document is a clinical investigational plan for a human research study. The study will be conducted in compliance with all stipulations of this protocol, the conditions of IRB approval, federal and local regulatory requirements, the Declaration of Helsinki, ISO-14155 and International Conference on Harmonization Good Clinical Practice guidance ICH GCP.

1.1 Background and Rationale

Anesthesia and brain monitoring in pediatric patients

Monitoring vital signs (pulse rate, respiratory rate, blood pressure, and temperature), respiratory and anesthesia parameters is considered standard for managing patients during anesthesia. However, the end target organ of action for anesthetic agents (the brain) is not routinely monitored.

In the last couple of decades a number of monitors (and/or indices) for monitoring depth of anesthesia were validated by examining measures of association between the index and either steady-state anesthetic concentration, and arousal. The performance of Bispectral index (BIS), state entropy/response entropy and the Narcotrend index has been published in a large number of adult studies. In general, no particular index has been shown to be substantially superior in these studies.

Use of brain function monitoring has been shown to improve clinical outcomes, by decreasing recovery and emergence times [1]. Although brain function monitoring has been in use for more than 15 years, it has not become a standard of care as confounding factors such as polypharmacy, low EEG power; EEG dynamics versus age and patient temperature were not included in the original training data set. This can lead to reduced accuracy under these conditions.

EEG-based monitors such as BIS and Patient State Index (PSI[™]) have been shown to be useful in assessing brain activity during sedation and general anesthesia. Though both indices have shown predictive value in assessing levels of sedation/awareness, there has only been marginal correlation between the two. [2, 3]

All information used by these brain function monitors has been derived from adult EEG data where the difference between the EEG when awake and the EEG when anaesthetized is obvious. The EEG in awake children is well described and steadily changes with maturation, but our knowledge of the EEG during anesthesia in children is scant and at this stage too limited to make any assumptions about extrapolating adult data to children. Therefore they ought to be assessed specifically in children.

There is little, but increasing, evidence that these devices work in older children, and that in older children they may improve some outcomes.

The SedLine Monitor

The SedLine® (Masimo Corporation, Irvine, CA) technology is based on more than 15 years of technical and clinical development. The device uses a multivariate algorithm to assess the patient's EEG data from all 4 channels and determine the Patient State Index (PSI™) value as a measure of anesthetic depth. The PSI was developed as a measure of hypnosis during anesthesia delivery and is based on quantitative electroencephalogram features, recorded from anterior scalp sites, as input to a multivariate algorithm that quantifies the most probable level of hypnosis. The PSI has a range from 0 (suppression of EEG) to 100 (fully

awake), with decreasing values indicating increasing levels of hypnosis. A PSI range of 25-50 indicates an adequate hypnotic state for general anesthesia. It has been demonstrated that the PSI has a significant relation to level of hypnosis, as measured by standard scales for quantifying level of alertness and sedation during intravenous propofol anesthesia as well as during inhalation anesthesia using isoflurane, sevoflurane, and desflurane. [4]

The PSI algorithm was constructed following a systematic study of the quantitative electroencephalogram changes that accompanied loss and return of consciousness and the most probable underlying sources of those changes, leading to hypotheses about the role of cortical and subcortical structures—systems in the maintenance of the conscious state and the development of the algorithm. [4-6]

. The sensor technology was developed to improve the acquisition of EEG signals and was used in NASA's Sleep Studies in 1998. By providing an integrated algorithm based upon 4-channels of EEG data, demonstrated reliability under challenging clinical conditions and superior resistance to cautery, the SedLine monitor system offers a cost-effective alternative to other monitors. The system is currently in use at some of the nation's leading healthcare institutions.

The SedLine Monitor consists of a SedLine Module that calculates the PSI using the EEG signals acquired from the EEG Sensor Array. A Graphical User Interface called Root displays raw EEG waveform and processed information including PSI.

SedLine® brain function monitoring for the Root™ patient monitoring platform helps improve anesthetic management by providing: a) four simultaneous EEG channels enable continuous assessment of both sides of the brain; b) a single sophisticated algorithm for Patient State Index (PSI™) about a patient's response to anesthesia; c) superior resistance to electrocautery minimizes signal drop out and d) multiple screen views expand information while enabling customization in the OR and ICU.

The SedLine module easily plugs into the Root patient monitoring platform via Masimo Open Connect™ (MOC-9™) ports.

The SedLine sensor is designed for ease in application and enhanced patient comfort while ensuring the highest quality data. Four active leads collect higher volume of data in key areas of frontal lobe. The sensor was designed for quick and easy application.

Since EEG data recording in pediatric patients under anesthesia and sedation is limited, we intend to collect high resolution EEG data using a SedLine Monitor in pediatric patients and over a wide range of anesthetics. Additionally, in order to assess the impact of anesthetic drug administration on vital sign parameters routinely used during anesthesia, we intend to collect other noninvasive parametric data including blood pressure, temperature, oxygen saturation and respiratory rate. Blood pressure and temperature will be recorded from the hospital's standard of care devices, while oxygen saturation and respiratory rate will be collected using Masimo Rainbow® Pulse CO-Oximeter devices. Masimo Rainbow® is a noninvasive monitoring platform enabling the assessment of a wide range of blood constituents and physiologic parameters such as total hemoglobin (SpHb), Oxygen Saturation (SpO2), Pulse Rate (PR), Perfusion Index (PI).

The inclusion of standardized clinical observations, acquisition of raw and processed physiological data, and anesthesia records used singularly or in combination will provide an opportunity to objectively evaluate the

performance of the current and future SedLine/Brain function monitoring algorithms under a wide range of clinical and patient conditions. It will also address limitations with collecting these data during sedation and general anesthesia.

Masimo's SedLine monitor is FDA cleared, noninvasive and is considered to be non-significant risk. Masimo Pulse CO-Oximeter sensors and devices are FDA cleared and considered to be non-significant risk as well. The SedLine Pediatric sensor is an investigational device that is being developed for pediatric use. The SedLine Pediatric sensor uses the same materials and intended use as the FDA-cleared SedLine adult sensor.

1.2 Study Devices

- FDA-cleared Radical-7 and Root[™] Rainbow Technology Multi-Function Docking Station (Masimo Corp) equipped with Patient State Index(PSI), Oxygen Saturation, Pulse Rate, and Perfusion Index.
- FDA-cleared SedLine patient modules
- Investigational SedLine forehead EEG sensors for pediatric use
- Masimo SET Pulse CO-Oximeter sensors (optional)
- Cables for use with Radical-7 and Root devices
- Laptop computer with
 Automatic Data Collection (ADC) (data collection software)

2 STUDY DESIGN AND OBJECTIVES

The primary objective is to collect SedLine EEG data along with head size measurements, vital signs, patient demographics, anesthetic record and surgical procedure data during general anesthesia or sedation. There are no endpoints of this study as data collection will be used for product development.

Data will also be collected using the SedLine array or KittyCat electrodes in order to collect EEG data on the younger pediatric population along with head size measurements, vital signs, anesthetic record and surgical procedure during general anesthesia or sedation for product development.

4 SUBJECT SELECTION AND WITHDRAWAL

4.1 Number of Subjects

Up to 220 pediatric subjects undergoing general surgery may be enrolled into this study. Up to 120 subjects will be enrolled between age 12 months and 17 years and up to 100 subjects with ages less than 12 months.

4.2 Inclusion Criteria

- Patients 17 years old and younger.
- ASA status I, II, or III.

 Scheduled for surgical and non-surgical procedures scheduled under general anesthesia or sedation (Common procedures include but are not restricted to tonsillectomy, adenoidectomy, urological procedures, dental rehabilitation, orthopedic procedures, biopsies, audiogram, nuclear scans, gastroscopy, colonoscopy, etc. Surgery can be open, laparoscopic, or robotic).

4.3 Exclusion Criteria

- Any deformities or devices that may prevent application of SedLine Array to forehead with a proper fit.
- Cases in which a rapid sequence induction is indicated (emergency, full stomach precautions).
- Subjects who are developmentally delayed.
- Subjects deemed not suitable for study at the discretion of the investigator.

4.4 Study Timelines

Each individual patient will participate in one study visit. Each study visit may start only after the informed consent has been obtained. The study visit will end in the PACU upon patient wake up from anesthesia, at which point data collection is considered complete.

4.5 Subject Recruitment and Screening

Following identification of a potential subject, the patient's parent or guardian will be approached by the principal investigator or a designated research staff member, who will explain the purpose and procedures of the study. If the patient's parent or guardian expresses interest in participating in the study, they will be asked to read the written Informed Consent Form in English or Spanish depending on their language preference.

All items of the Informed Consent will be explained in a way that is easily understandable for either English or Spanish speaking subjects. The patient's parent or guardian will be given adequate time to read through the Informed Consent, and they will be given adequate time and privacy to consider the decision of whether or not to sign the Informed Consent Form and have their child participate in the study. If the patient is within age requirements for Assent, the patient will need to read and sign the Assent Form. Once the patient's parents and guardians questions have been answered and the Informed Consent Form and Assent (if applicable) is signed, the patient is now adequately consented. Now the patient will be enrolled as a study subject, at which time the subject will be assigned a study identification number or enrollment number.

All subjects will have their medical history reviewed at the time of screening by either the PI or the study staff who is delegated for this task. Subjects will be evaluated based on the inclusion and exclusion criteria to determine eligibility to be enrolled into the study. If a subject is deemed ineligible after screening, the subject will be withdrawn from the study.

Information regarding the subject's demographic (including, but not limited to age, weight, race, ethnicity, comorbidities, medications, etc.), preexisting allergies, skin abnormalities, and other preexisting diseases/conditions that may be relevant to the study will be recorded on the Case Report Form (CRF).

HIPAA

The pre-screening of patients will require the investigators to access personal health information to identify prospective subjects without HIPAA authorization prior to obtaining written informed consent for the study. Informed consent and HIPAA authorization will be obtained during recruitment and screening procedures as

described in previous sections of this clinical investigation plan (HIPAA authorization is included in the same form as the Informed Consent); however, pre-screening process would require the IRB to grant a waiver of HIPAA authorization, as the research study could not be practicably carried out without this implied waiver of consent. The participants' rights and welfare will not be adversely affected by waiving consent. Patients' protected health information (PHI) will not be inappropriately reused or disclosed to any other person or entity. To further safeguard all protected health information, the data collected during the study will not be labeled with any personal identifying information. The data will not be stored with any protected health information identifiers.

4.6 Withdrawal of Subjects

Any refusals or withdrawals from the study will be documented, with the reason recorded. The investigator or treating anesthesiologist may withdraw a patient from the protocol if it is deemed it is no longer feasible to continue the study or that the continuation of the study will affect the subject's safety and well-being.

Participants are free to withdraw from the study at any time. Parents will be informed that a refusal to take part in the study will not alter the clinical treatment of their child.

4.7 Vulnerable populations

Vulnerable populations that may be enrolled in this study include children and non-English speakers. To protect children, patients and parents/guardians will be provided with adequate time to read the informed consent and to have their questions answered. Assent forms will be provided to age-appropriate subjects as required by the IRB, and by obtaining parental/guardian permission from one parent as required by the IRB. To protect non-English speaking subjects, informed consent and assent forms in their native language will be provided. As only Spanish-speaking subjects are anticipated to be enrolled in the study, informed consents and assents in Spanish will be provided to the subjects and their parents/guardians. The site will also have Spanish speaking translators available to help verbally answer any of the subject's questions.

The IRB will review research with vulnerable populations and evaluate consent, level of risk, coercion, and the reason for choosing this particular subject population. The IRB will be responsible for determining what practices will include continuing review for compliance while monitoring these studies.

The Investigator holds the ultimate responsibility for protecting the rights, safety, and welfare of research subjects by ensuring that all regulations and proper documentation of consent is handled in a compliant and timely manner.

5 STUDY DEVICES

Investigational Devices:

• Masimo SedLine Pediatric Sensor: this sensor is identical to the adult sensor in materials but has been reduced in size to fit the pediatric population.

FDA-cleared Devices:

Masimo Radical-7 and RootTM Rainbow Technology Multi-Function Docking Station (Masimo Corp)
equipped Oxygen Saturation (SpO2), Pulse Rate (PR), Perfusion Index (PI), Pleth Variability Index (PVI),
and current/FDA approved Patient State Index (PSI).

- SedLine patient modules, cables, and adult sensors.
- Masimo SpO2 sensors (optional)
- Up to 10 Medtronic KittyCat Electrodes with leadwires

Data Acquisition

- Neuroscan EEG Data Acquisition System
- Laptop computer with data collection software both Automated Data Collection software (Masimo Corp)

5.1 Device Accountability

5.1.1 Receipt of Study Device

Upon receipt of the of the study device, an inventory must be performed and the device accountability log filled out and signed by the person accepting the shipment. It is important that the designated study staff counts and verifies that the shipment contains all the items noted in the shipment inventory. Any damaged or unusable study devices in a given shipment will be documented in the study files. The investigator must notify the study sponsor of any damaged or unusable study devices that were supplied to the investigator's site.

5.1.2 Use of Study Device

Use of devices and sensors will be documented on case report forms for each subject.

5.1.3 Return or Destruction of Study Device

At the completion of the study, there will be a final reconciliation of study devices and sensors shipped, devices/sensors used, and devices/sensors remaining. This reconciliation will be logged on the device accountability log. Any discrepancies noted will be investigated, resolved, and documented prior to return or destruction of unused study devices. Devices destroyed on site will only be upon written instruction from the sponsor and will be documented in the study files.

6 STUDY PROCEDURES

At any time during study procedures, at the discretion of the anesthesiologists and/or anesthesia providers, they can discontinue study procedures and exercise clinical judgment to safeguard the subject's health, safety, and welfare. EEG data from the investigational SedLine pediatric sensor or KittyCat electrodes will not be used to guide clinical care or decisions. The study procedures described below are within the institution's standard of care anesthesia procedures.

6.1 Pre-Induction

The SedLine pediatric sensor array is comprised of four (4) central electrodes and two (2) lateral electrodes (See Figure 1). For subjects between 13 months and 17 years, the pediatric SedLine sensor array will be applied according to manufacturer's directions for use before premedication or start of anesthesia. Up to 4 KittyCat electrodes will be applied at BIS Sensor locations for on-label BIS XP with both right and left forehead placements. There are no standardized location identifiers for BIS sensor placements except for being adjacent

to the SedLine EEG sensor as shown in Figure 2. Both the SedLine EEG Sensor and the additional KittyCat Electrodes are connected
For subjects 12 months or younger, either the SedLine pediatric sensor array or the KittyCat electrodes will be applied to the subject. If the SedLine sensor is not used, 6 KittyCat electrodes may be placed in similar locations to the SedLine sensor array. An additional 4 BIS sensor placements will be optional depending on the amount of available space on the subject's forehead as determined by the PI and/or research staff. These KittyCat electrodes will be connected the SedLine module.
At application each lead will be checked to make sure impedance of each of SedLine channel is less or equal to in all electrodes. Good contact is indicated by a green or yellow color on the electrode status display on Root. Upon a successful impedance test, the impedance test will be turned off. Baseline EEG will be recorded for approximately 3 minutes. SedLine and SpO2 sensors may be placed on the subject and connected to the Radical 7 and/or Root during pre-op or before anesthesia. The SpO2 sensor's usage will be optional in this study. Data will be recording in Automated Data Collection (ADC) software. The SedLine sensor and other sensors may be disconnected during transportation of the patient and reconnected in the operating room.
6.2 Anesthetic Protocol
Induction is defined as the interval between the initial administration of the anesthetic agent until the patient is deemed ready for the airway to be secured by the anesthesiologist and, if necessary, intubation, is complete. After IV induction or inhalation (sevoflurane or propofol) induction, anesthesia will be maintained using either sevoflurane or propofol (approximately 50% of patients will be in each group).
The exact dose and time of administration of all gases and all medications that directly or indirectly target the brain and muscles (e.g. muscle relaxants) will be recorded throughout the anesthesia and continued into the recovery period until the end of the study. All concomitant medications given between the time the EEG electrodes are applied and removed are to be recorded.
Sevoflurane for Maintenance
In patients receiving sevoflurane for induction and maintenance following IV catheter insertion, sevoflurane will be administered when feasible in up to 3 steps in order to achieve a stable end-tidal sevoflurane concentration of The order of these 3 steps will be assigned randomly prior to induction of anesthesia. In addition, nitrous oxide may be used during induction and maintenance of anesthesia, and fentanyl or remifentanil may also be used.
Step Changes is defined as the phase immediately following induction and intubation, if applicable. Sevoflurane, either with or without N2O, will be administered during step changes with no changes to either sevoflurane or N2O during the step change interval.
The anesthesiologist will increase and/or decrease the target anesthesia drug in a stepwise manner and hold for steady state at the target age adjusted MAC for each of the following

concentrations as indicated in Table 1. Steady state is defined as the target end-tidal concentration \pm 0.1% for sevoflurane. The lightest MAC step will be discontinued if signs of "light" anesthesia are observed; however, the anesthesiologist at his/her discretion may continue to collect step change data at higher target effect site concentration in accordance with the protocol.

Table 1

Target MAC (Minimum Alveolar Concentration) Step Changes				
Scheme 1	Scheme 2	Scheme 3		

Table 1: 1 MAC is 2.5% for children 6 months - 10 years of age, and 2% in children over the age of 10 years (from Cote CJ, Lerman J, Anderson BJ. A Practice of Anesthesia for Infants and Children, 5th ed, p. 101-2, Elsevier Saunders, Philadelphia, PA; 2013)

Whenever feasible, the maintenance anesthetic agent (sevoflurane) will be reduced at the end of the surgical procedure in a step-wise fashion, with each step at least 5 minutes in duration. Examples include sevoflurane 4% - 3% - 2% - off.

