7 SAMPLE SIZE AND STATISTICAL CONSIDERATIONS

The purpose of data collection is an observational study to build a database of representative PSI signal profiles for the pediatric population under select conditions. Sample size is therefore non-deterministic by normal

sampling means. Approximately 220 subjects will be enrolled in the study. Site should do its best to achieve sufficient enrollment in all age groups.

Age		
12 months and		
younger		
13-35 months		
3-5 years		
5-11 years		
11-17 years		

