9.5 Case Report Forms

- 9.5.1 The Sponsor shall provide a Case Report Form (CRF) template to the Site. The Site shall capture study data in the CRFs for each subject enrolled. The CRFs will be reviewed and signed by principal investigator. This also applies to those subjects who fail to complete the study. If a subject withdraws from the study, it is highly recommended that the reason(s) be noted on the CRF. Case report forms are to be completed on an ongoing basis. CRF entries and corrections will only be performed by study site staffs that are authorized by the investigator. Entries and corrections to the CRF will be made following Good Documentation Practices.
- 9.5.2 The CRF will include the following information, including but not limited to: inclusion / exclusion criteria, whether patient consent obtained before start of study, demographic information, event timing, anesthetic drugs used and dosage, patient skin condition after sensor removal, etc.
- 9.5.3 The CRF will be signed by the PI, and securely transferred to Masimo in pdf format.
- 9.5.4 CRF entries will be checked by Sponsor personnel after receipt and any errors or inconsistencies will be queried to the site on an ongoing basis. Query resolution will be assessed and confirmed by study monitor during site visit.

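### Does the MAC note under Table 1, which starts at 6 months of age, leave the sevoflurane steps unusable for younger infants?

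*Combined protocol and SAP*

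**What the plan says.** Section 6.2 of the combined protocol and SAP asks the anesthesiologist to change sevoflurane in steps after induction and to "hold for steady state at the target age adjusted MAC". It adds: "Steady state is defined as the target end-tidal concentration", with a tolerance of ±0.1%. The note under Table 1 supplies the conversion from MAC to percent: "1 MAC is 2.5% for children 6 months - 10 years of age, and 2% in children over the age of 10 years", followed by a textbook citation with page numbers. No value for infants under 6 months is visible.

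Eligibility is wider than the note. Section 4.2 admits "Patients 17 years old and younger", Section 4.1 allows "up to 100 subjects with ages less than 12 months", and none of the exclusions in Section 4.3 is an age limit. On the choice of maintenance agent, sevoflurane or propofol, Section 6.2 says "approximately 50% of patients will be in each group".

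Section 2 states that the study has no endpoints and serves product development. Section 7 gives the aim as to "build a database of representative PSI signal profiles for the pediatric population under select conditions", and its youngest age group is 12 months and younger. Section 6.2 requires the dose and time of every gas to be recorded, and the case report form in Section 9.5 lists "anesthetic drugs used and dosage".

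**The concern.** A MAC target becomes an end-tidal percentage only through a 1-MAC value for the child's age. If that value is missing below 6 months, the visible text fixes neither the concentration to hold nor the centre of the ±0.1% window. Two anesthesiologists using different references could hold different concentrations and both record the same nominal step.

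The youngest age group in Section 7 straddles the 6-month boundary. It could therefore mix steps that have a documented conversion with steps whose conversion was chosen locally. In a database meant to describe signal profiles under chosen conditions, that would weaken comparisons within the group. Infants under 12 months may be up to 100 of 220 subjects, so the point deserved a check.

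**Working it through.** **Enrolment total.** Section 4.1 gives up to 120 subjects from 12 months to 17 years and up to 100 younger: 120 + 100 = 220, as stated. Infants under 12 months are at most 100/220 = 45.5%.

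**Age coverage, side by side.**

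| Source | Ages covered |
|---|---|
| Sections 4.1 to 4.3, eligibility | up to 17 years, no lower limit |
| Section 6.2, note under Table 1 | 6 months to 10 years (2.5%); over 10 years (2%) |
| Section 6.2, who has steps | patients with sevoflurane for induction and maintenance, where feasible, at most 3 steps; no age stated |

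The eligibility sections govern the whole data collection. No section says that every eligible child must have steps. The sections are therefore silent about infants under 6 months; they do not contradict one another.

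**What the visible text lets one derive.** If the target is k × D, with k the MAC multiple and D the 1-MAC value, the window is k × D ± 0.1. The product form is itself an inference, because the sentence that states the end-tidal concentration directly is also blank.

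- From 6 months up, D is visible but k is not. For illustration at k = 1, the windows are 2.5 ± 0.1 = 2.4 to 2.6% and 2.0 ± 0.1 = 1.9 to 2.1%.
- Under 6 months, neither D nor k is visible. Only the half-width of 0.1 is known.

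No actual step target can be computed from the public copy at any age. What is specific to the youngest infants is one conversion value.

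**How much a different reference would matter.** Two windows built on D1 and D2 stop overlapping when k × |D1 − D2| > 0.1 + 0.1 = 0.2 vol%. With assumed multiples:

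- k = 0.5: 0.2/0.5 = 0.40 vol%
- k = 1: 0.2/1 = 0.20 vol%, which is 0.2/2.5 = 8% of the 2.5% value
- k = 1.5: 0.2/1.5 = 0.13 vol%

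The protocol's two values differ by 2.5 − 2.0 = 0.5 vol%, so their windows are disjoint for any k above 0.2/0.5 = 0.4. This shows that the rule is sensitive to the reference. It does not show that clinicians would disagree below 6 months.

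**How many infants.** The share of infants under 6 months (s) is not given. Applying the study-wide sevoflurane share of about 50% to infants is an assumption. The number is 100 × 0.5 × s:

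| s | Infants | Of 220 |
|---|---|---|
| 0 | 0 | 0% |
| 0.25 | 12.5 | 5.7% |
| 0.5 | 25 | 11.4% |
| 1 | 50 | 22.7% |

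These figures scale with the sevoflurane share among infants. They would fall because steps apply only when sevoflurane is used for both induction and maintenance and only where feasible, and because eligibility also includes sedation.

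**What uses the MAC label.** Section 2 names no endpoint, and Section 7 gives no test, estimate or power calculation. No stated result depends on a MAC value.

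**The case for a change.** The strongest case for a change is this. The note reads as complete, running without a break from its two age bands into its citation. The blank Table 1 cells sit under a heading about MAC targets with no age column, so they may not hold the missing conversion. Where the protocol wants infants handled differently it says so, as with the electrode rule for subjects 12 months or younger in Section 6.1; Section 6.2 has no such rule. Recorded doses describe what was given but cannot create steps at a common target that were never held. Sections 6.7 and 9.5 do not name measured end-tidal concentration as a recorded item. One sentence would close the gap.

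Part of this stands. The visible text has no conversion below 6 months, and later records cannot replace steps that were not run at a common target.

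The rest is weaker. A second blank, where Section 6.2 states the end-tidal concentration itself, could cover these infants, and what is blank in the public copy cannot be counted as missing from the plan. The note cites a reference that sites can share; whether its pages cover younger infants cannot be checked here, but it is not shown that each anesthesiologist would choose alone. Equal sevoflurane MAC would not by itself make steps comparable, since Section 6.2 allows nitrous oxide, fentanyl or remifentanil and Section 6.6 excludes no medication. Extra form fields for end-tidal percentage and the reference used are a documentation preference, and the anesthesia record may already hold the former.

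**Conclusion.** No change to the plan follows. The observation is correct in a narrow form: the visible note starts at 6 months, eligibility does not, and no visible text says whether or how the MAC steps apply to younger infants. This is missing detail that practice can fill sensibly; no stated rule gives a wrong result.

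Analysts can sort the records by the gas doses and times that Section 6.2 requires, and can describe infants under 6 months separately within the youngest group. No endpoint, error rate or sample size is touched. The only exposure is to the labelling and comparability of some step records. It ranges from 0 to about 50 infants, assuming a 50% sevoflurane share in infants, with 25 if half of them are under 6 months; all of these are before the reductions for feasibility and induction agent. The further claim that windows would fail to overlap rests on assumed multiples and assumed disagreement between clinicians.

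The sponsor, who holds the full text, can see whether the blank parts already align the note's age coverage with Sections 4.1 and 4.2. No concentration or clinical rule is suggested here.
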